Table 12	QT prolongations in ECG parameters	33
Table 13	Analysis visit windows.....	42
Table 14	Thresholds for marked laboratory abnormalities	65

LIST OF FIGURES

Figure 1	Study design and flow	10
----------	-----------------------------	----

LIST OF APPENDICES

Appendix A	Protocol synopsis.....	58
Appendix B	Visit and assessment schedule.....	63
Appendix C	Discussion and further considerations of the applied statistical methods	65
Appendix D	Definitions of marked abnormalities and elevated liver function tests	65
Appendix E	Mock layout.....	66
Appendix F	Document history	135

LIST OF ABBREVIATIONS AND ACRONYMS

AE	Adverse event
ADaM	Analysis data model
ALT	Alanine aminotransferase
AP	Alkaline phosphatase
AST	Aspartate aminotransferase
ATC	Anatomic Therapeutic Chemical
AUC _{τ, ss}	Area under the plasma concentration-time curve during a dose interval at steady state
b.i.d.	Twice daily
BLQ	Below limit of quantification
CDISC	Clinical data interchange consortium
CI	Confidence interval
C _{max, ss}	Maximum plasma concentration at steady state
CSR	Clinical study report
C _{trough, ss}	Trough plasma concentration at steady state
CV	Coefficient of variation
CV _b	Inter-subject coefficient of variation
DBP	Diastolic blood pressure
ECG	Electrocardiograph
eCRF	Electronic case report form
EOS	End-of-study
EudraCT	European Union Drug Regulating Authorities Clinical Trials
IB	Investigator's Brochure
i.v.	Intravenous
ivSAF	intravenous Safety Analysis Set
LOQ	Limit of quantification
MedDRA	Medical Dictionary for Regulatory Activities
MSE	Mean squared error
PAH	Pulmonary arterial hypertension
PDs	Protocol deviations
PK	Pharmacokinetic
PKS	Pharmacokinetic Analysis Set
PR	Pulse rate

PT	Preferred Term
QTcB	QT interval corrected using Bazett's formula
QTcF	QT interval corrected using Fridericia's formula
RMP	Risk Management Plan
SAE	Serious adverse event
SAF	Safety Analysis Set
SAP	Statistical analysis plan
SAS®	Statistical Analysis Software
SBP	Systolic blood pressure
SCR	Screened Analysis Set
SD	Standard deviation
SDTM	Study data tabulation model
SE	Standard error of the mean
SOC	System organ class
$t_{\max, ss}$	Time to reach maximum plasma concentration at steady state
WHO	World Health Organization
WHO FC	WHO functional class
WHODD	WHO Drug Dictionary

1 INTRODUCTION

This statistical analysis plan (SAP) describes in detail the derivation of safety and pharmacokinetic (PK) endpoints and the analyses and the presentation of analysis results and data for the clinical study report (CSR) of study AC-065A309.

Study data tabulation model (SDTM) datasets, including data from central labs and PK data provided by Actelion Data Management will be considered source data. Technical procedures and steps for processing these data and for implementing the definitions of variables for the purpose of the statistical analysis in analysis data model (ADaM) datasets will be covered in the analysis datasets specifications document.

In this SAP, 'Uptravi®' refers to the prescribed presentation of oral selexipag; whereas 'i.v. selexipag' refers to the intravenous (i.v.) presentation of selexipag, which is considered the study drug.

This SAP is based on the following study documents:

Table 1 Study documents

Document	Date, Version
Study Protocol	27JAN2017, Version 1 19APR2017, Version 1.DEU.A (local)
eCRF specifications	22SEP2017, Version 5
Protocol deviation code list	22FEB2017, Version 1.0
Selexipag (Uptravi®) EU Risk Management Plan	21JUN2017, Version 5.4
ECG data transfer specification	18AUG2017, Version 1.0
Definition of Marked Abnormalities in Laboratory Data (OTH-000005)	01NOV2017, Version 9

2 STUDY DESIGN AND FLOW

2.1 Study design

This is a prospective, multi-center, open-label, single-sequence, cross-over, Phase 3 study.

Approximately 20 subjects with stable pulmonary arterial hypertension (PAH), currently treated with Uptravi (oral selexipag) at a stable dose, i.e., unchanged dose for at least 28 days, will be enrolled in order to obtain 18 evaluable subjects. Subjects will be stratified based on their stable Uptravi dose:

- Group A: Subjects with a stable dose of Uptravi between 200 and 1000 µg twice daily (b.i.d.) (inclusive); at least 5 and up to 8 subjects will be enrolled in this dose group.

- Group B: Subjects with a stable dose of Uptravi between 1200 and 1600 µg b.i.d. (inclusive); at least 12 and up to 15 subjects will be enrolled in this dose group.

The study will be conducted at approximately 10 sites in 2 countries.

2.2 Study visit and assessment schedule

The study visit and assessment schedule is included in [Appendix A](#).

2.3 Analysis periods

The study comprises five analysis periods:

Screening period: This period starts with the signing of the Informed Consent Form and ends with the first day of Period 1 (Visit 2 Day 1).

Period 1 (Uptravi, pre-treatment period, in-hospital): This period starts with intake of the morning dose of Uptravi at Visit 2 Day 1, and ends the following day before initiation of the first infusion of i.v. selexipag.

Period 2 (i.v. selexipag, treatment period, in-hospital): This period starts in the morning of Visit 2 on Day 2 with the start of the first infusion of i.v. selexipag, and ends after approximately 36 hours in the evening of Visit 2 on Day 3 with the resuming of administration of Uptravi at the evening dose.

Period 3 (Uptravi, post-treatment period): This period starts in the evening of Visit 2 Day 3 with the first dose of resumed oral administration of Uptravi, and ends 7 to 11 days later at Visit 3.

Safety follow-up period: This period starts at the end of Visit 3 and ends 30 to 37 days after the last administration of i.v. selexipag with the End-of-Study (EOS) telephone call (Visit 4).

[figure not shown]
A summary of analysis periods is presented in [Table 2](#):

Table 2 Summary of analysis periods

Period	Start	Stop
Screening period	Date/time of first Informed consent form signature	Prior to morning dose of Uptravi at Visit 2 Day 1
Period 1: Uptravi, pre-treatment period	Date/Time of Uptravi morning dose intake at Visit 2 Day 1	Prior to start of first infusion of i.v. selexipag at Visit 2 Day 2
Period 2: i.v. selexipag, treatment period	Start date/time of first infusion of i.v. selexipag at Visit 2 Day 2	Prior to evening dose of Uptravi at Visit 2 Day 3
Period 3: Uptravi, post-treatment period	Date/time of Uptravi evening dose intake at Visit 2 Day 3	Visit 3
Safety follow-up period	After end of Visit 3	End of Study

The study design and flow is shown in Figure 1 below. For details, refer to section 3 and section 7 of the AC-065A309 study protocol [D-17.055].

Figure 1 Study design and flow

* 12-hour PK profile after the morning dose.

** For convenience, hospitalization may be extended to the night before Day 1 and to the night of Day 3.

D = day; EOS = End-of-Study; IV1–IV3 = dose of i.v. selexipag; PK = pharmacokinetic; V = visit.

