3.1.1 Study periods

The study comprises the following consecutive periods:

Screening period:

Up to 28 days; starts with the signing of the Informed Consent Form (ICF) and ends with first day (Visit 2, Day 1) of Period 1 (Uptravi, pre-treatment period).

Treatment and observation period:

The treatment and observation period includes the following consecutive periods:

- Period 1 (Uptravi, pre-treatment period, in-hospital): 1 day
Starts with intake of the morning dose of Uptravi at Visit 2 Day 1 and ends the following day, before initiation of the first infusion of i.v. selexipag.
- Period 2 (i.v. selexipag, treatment period, in-hospital): 36 hours (3 doses)
Starts in the morning of Visit 2 on Day 2 with the start of the first infusion of i.v. selexipag and ends in the evening of Visit 2 on Day 3 before the evening administration of Uptravi. Note: oral administration of Uptravi is interrupted during the treatment period with i.v. selexipag.

- Period 3 (Uptravi, post-treatment period): 7 to 11 days
Starts in the evening of Visit 2 Day 3 with the oral administration of Uptravi and ends 7 to 11 days later, at Visit 3.

[figure not shown]
Safety Follow-up period:

Starts at the end of Visit 3 and ends 30 to 37 days after the last administration of i.v. selexipag with the End-of-Study (EOS) telephone call (Visit 4).

The visit schedule and protocol-mandated procedures will be performed according to the table of assessments [Table 2] and are described in Section 7.

The overall study design is depicted in Figure 1.

Figure 1 Study design

* 12-hour PK profile after the morning dose.

** For convenience hospitalization may be extended to the night before Day 1 and to the night of Day 3.

D = day; EOS = End-of-Study; IV1–IV3 = dose of i.v. selexipag; V = visit

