5.1.9 Study treatment dose adjustments and interruptions

The i.v. selexipag dose corresponding to subject's stable Uptravi dose is expected to be fully infused each time and adjustment of i.v. selexipag dose is not allowed in this study.

Confidential

Missing any of the 3 scheduled i.v. selexipag infusions is not allowed. If one or more of the i.v. selexipag infusions is missed, re-introduction is not permitted and i.v. selexipag treatment must be permanently discontinued [see Section [5.1.10](#)]. Uptriavi may be reintroduced after stopping i.v. selexipag, at the next scheduled dosing time point, if deemed medically needed for the subject.

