5.1.10 Premature discontinuation of study treatment

A subject is considered as having prematurely discontinued study treatment if the third i.v. selexipag infusion was not initiated.

The decision to prematurely discontinue i.v. selexipag treatment may be made by the subject, the investigator or Actelion personnel. The main reason and whether discontinuation of i.v. selexipag treatment is the decision of the subject (e.g., tolerability- or efficacy-related), the investigator (e.g., due to pre-specified i.v. selexipag treatment discontinuation criteria, an AE or lack of efficacy), or Actelion (e.g., study terminated) must be documented in the CRF.

A subject has the right to discontinue i.v. selexipag treatment at any time, without any justification, by withdrawal from study treatment only or by withdrawal from any further participation in the study (i.e., premature withdrawal from the study [see Section [8.2](#)]). Although a subject is not obliged to provide his/her reason for prematurely withdrawing from the treatment or the study, it is recommended that the investigator makes a reasonable effort to ascertain the reason(s), while fully respecting the subject's rights.

The investigator must discontinue i.v. selexipag treatment for a given subject if, he/she believes that continued administration would be contrary to the best interests of the subject.

Study-specific criteria for discontinuation of i.v. selexipag treatment are described in Section [5.1.11](#).

A subject who prematurely discontinues i.v. selexipag treatment is to be discontinued from the study. For safety reasons, it is recommended to perform the assessments of Visit 3. The EOS telephone call (Visit 4) must be performed, provided that the subject's consent for this limited participation in the study has not been withdrawn. The assessments that are to be performed at each visit are described in [Table 2](#).

A subject who prematurely discontinues i.v. selexipag treatment and withdraws consent to participate in any further study assessments is considered as withdrawn from the study. Subjects who die or are lost to follow-up are also considered as withdrawn from the study. Withdrawal from the study and follow-up medical care of subjects withdrawn from the study is described in Sections [8.2](#) and [8.4](#), respectively.

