6. If Visit 1 and Visit 2 Day 1 are performed within 7 days, laboratory tests do not have to be repeated at Visit 2 Day 1.
7. ECG will be performed at pre-dose and within 30 minutes after stopping of infusion (i.v. selexipag).
8. PK profile includes 7 blood samples. Timing of blood samples is detailed in [Table 3](#)
9. Infusion solution samples will be taken from the tubing before each infusion [see [Table 3](#)].
10. All AEs and SAEs that occur after signing the Informed Consent Form and up to 30 days after i.v. selexipag study treatment discontinuation must be reported.

Table 3 Visit 2 vital signs and PK blood collection schedule

	Visit 2 (hospitalization)														Period 3 (Uptravi, Post-treatment Period)								
	Period 1 (Uptravi, Pre-treatment Period)							Period 2 (Treatment Period; i.v. selexipag)															
	Day 1							Day 2							Day 3								
Time ¹ after morning dose	0 h	1 h	2 h	4 h	6 h	8 h	12 h	0 h	25 min	87 min	4 h	6 h	8 h	12 h	0 h	25 min	87 min	4 h	6 h	8 h	12 h		
Uptravi oral intake	X						X															X	
Infusion solution sample ²								X							X	X							
Selexipag i.v. infusion								X	—————>						X ⁵	X	—————>						
PK blood sample	X ³	X	X	X	X	X	X ³								X ³	X	X ⁴	X	X	X	X ³		
Vital signs (pulse rate and BP)	X							X ³	X	X ⁴	X	X	X	X ³	X ³	X	X ⁴	X	X	X	X ³		

BP = blood pressure; i.v. = intravenous; PK = pharmacokinetic.

¹ A time window of \pm 5% is allowed for PK time points.

² Infusion solution sample will be taken from the tubing prior to selexipag infusion.

³ Vital signs and PK blood sample must be assessed/taken before selexipag administration (oral or i.v.).

⁴ Immediately before stopping the infusion.

⁵ Evening i.v. selexipag infusion to be started 12 h \pm 1 h after the start of the morning infusion.

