7.2.2 Analysis

The start date/time of the AE record from the CRF will be used to assign the AE to a study period.

Summary tables will be prepared as described in [Table 8](#) for the periods mentioned in [Table 7](#), except for the screening period.

Summary tables by SOC and PT will display the number and percentages of subjects with at least one AE in the respective primary SOC and at least one AE at the PT level. Summaries will be sorted by descending total frequency of SOCs and PTs and alphabetically in case of ties.

Summary tables by PT will display the number and percentages of subjects with at least one AE in the respective PT. Summaries will be sorted by descending total frequency of PTs and alphabetically in case of ties.

AEs occurring during the Screening period, i.e., prior to first dose of Uptravi on Visit 2 Day 1, will be listed.

Due to the small number of subjects, conservative 95% Clopper-Pearson CIs for the proportions will be computed using exact methods.

All AEs occurring during the study from date of informed consent signature to EOS will be listed.

For any injection site reaction (irrespective of clinical significance), the worst grade, criteria of the injection site reaction, as well as its clinical significance will be summarized. Any AEs associated with clinically significant injection site reactions will be summarized by PT and by maximum intensity in the AE table.

Table 8 Overview of adverse event analyses

Category	Approach
All AEs	
- N (%) of subjects having at least one AE by primary SOC and PT- N (%) of subjects having at least one AE by PT- N (%) of subjects having at least one AE by PT and maximum intensity- Listing
SAEs	
- N (%) of subjects having at least one SAE by PT- Listing
Injection site reaction AEs	
- N(%), grade and diagnosis criteria of injection site reactions- N (%) of subjects having at least one clinically significant injection site reaction by PT and maximum intensity- Listing of PTs and specific details
Prostacyclin-associated AEs	
- N (%) of subjects having at least one prostacyclin associated AE by PT- N % of subjects having at least one prostacyclin associated SAE by PT- N % of subjects having least one prostacyclin associated AE leading to discontinuation of study drug by PT- Listing

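### SAP Table 2 fixes the Period 2/3 boundary at the Day 3 evening Uptravi dose, so for subjects who stop i.v. early up to about 24 h on resumed oral drug is counted as i.v. period

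*SAP*

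**What the plan says.** SAP 2.3 describes Period 2 as a period that "ends after approximately 36 hours in the evening of Visit 2 on Day 3 with the resuming of administration of Uptravi at the evening dose". SAP Table 2 gives its stop as "Prior to evening dose of Uptravi at Visit 2 Day 3" and the start of Period 3 as "Date/time of Uptravi evening dose intake at Visit 2 Day 3". Protocol 3.1.1 uses the same boundary.

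Protocol 5.1.9 covers the subject who misses an infusion. The i.v. drug is stopped for good, and Uptravi "may be reintroduced after stopping i.v. selexipag, at the next scheduled dosing time point", if there is a medical need. Protocol 5.1.10 defines the early stopper: "A subject is considered as having prematurely discontinued study treatment if the third i.v. selexipag infusion was not initiated".

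The period dates drive the by-period safety tables. SAP 7.2.2 states: "The start date/time of the AE record from the CRF will be used to assign the AE to a study period". SAP 10.2.4 assigns other assessments to periods through Table 2, by date and time.

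The only exception for non-completers is the footnote to protocol Table 4, which covers subjects who receive no i.v. dose at all. SAP 10.2.1 defines the end of study treatment as the end of the last infusion, but Table 2 does not use that definition.

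**The concern.** The boundary is written for a subject who receives all three infusions. One or two infusions are enough to place a subject in the i.v. Safety Analysis Set, and SAP 5.1.1 and 5.5.1.1 tabulate such subjects. Once a subject is back on Uptravi before the Day 3 evening, the label of Period 2 no longer matches the drug being taken. Any event that starts in that interval is still counted as an i.v.-period event.

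A second gap follows from the conditional wording in protocol 5.1.9. If the subject takes no Uptravi on the Day 3 evening, Period 2 has no stop and Period 3 has no start.

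Evaluating safety in each study period is a stated objective (protocol 2.2, SAP 3.2), and Period 2 alone is the most direct display of tolerability on the i.v. drug. The subjects affected are those who did not complete i.v. treatment.

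**Working it through.** **Inputs**
- Period 2 starts with the first infusion, taken as hour 0 (SAP Table 2).
- Dosing interval: "Evening i.v. selexipag infusion to be started 12 h" after the morning infusion starts, with a 1 h tolerance (protocol Table 3, footnote).
- Planned Period 2: three doses, 36 h (protocol 3.1.1).
- Size of the i.v. set: 18. Planning rate of prostacyclin-associated discontinuation: 5% to 10% (protocol 10.5, SAP 2.5).

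**The plan's own figure.** 3 doses × 12 h = 36 h, as stated. Infusions start at hours 0, 12 and 24, and the Day 3 evening Uptravi dose falls at hour 36.

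**Oral time counted in Period 2.** If Uptravi is resumed at hour *r*, the misassigned window is 36 − *r*.

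| Last infusion started | Uptravi resumed | *r* (h) | 36 − *r* (h) | Share of 36 h |
|---|---|---|---|---|
| 1 | Day 2 evening | 12 | 24 | 67% |
| 1 | Day 3 morning | 24 | 12 | 33% |
| 2 | Day 3 morning | 24 | 12 | 33% |
| 2 | Day 3 evening | 36 | 0 | 0% |
| 3 | Day 3 evening | 36 | 0 | 0% |
| 1 or 2 | no Day 3 evening dose | – | boundary undefined | – |

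Two rows appear for each early stop because the next scheduled time depends on when the stop is decided. If an infusion is missed at its due time, the next time point is 12 h later. All hours are approximate because of the 1 h tolerance.

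**Displays that depend on the boundary** (SAP Table 7). Period 2, Period 3&FU and Period 1&2 depend on it. Periods 2&3&FU and 1&2&3&FU contain both sides of it and do not change. The treatment-emergent definition (Period 2 onward) does not change either. An AE that led to stopping i.v. drug began before Uptravi was resumed, so the discontinuation counts stand.

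**Subjects affected.** This assumes that the 5–10% rate applies to early i.v. stops.
- Expected number: 18 × 0.05 = 0.9 to 18 × 0.10 = 1.8.
- Chance of at least one: 1 − 0.95^18 = 60% to 1 − 0.90^18 = 85%.

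**Effect on an incidence.** Tables count subjects with at least one event, so a subject adds 1/18 = 5.6 points to a row only if that row did not already include the subject in Period 2. With exact Clopper-Pearson 95% limits:
- 0/18: 0 to 18.5%
- 1/18: 5.6% (0.1% to 27.3%)
- 2/18: 11.1% (1.4% to 34.7%)

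The last upper limit matches the plan's 35% for the i.v. set. The same method gives 1.2% to 31.7% for 2/20, which matches its 32% for the Safety Set.

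**The case against.** The intended split can be read from the text. SAP 2.3 starts Period 3 with resumed oral dosing, and protocol 10.2.3.1 separates events by whether they fall before or after intake of oral or i.v. drug. On that view only a clarification for non-completers is missing. But both SAP 2.3 and Table 2 still tie the boundary to the Day 3 evening, and a programmer who follows Table 2 gets the wrong period. The intention does not repair the rule.

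Several other objections stand and limit the point:
- The 24 h figure is an upper value. Resumption is conditional and may come later.
- The 5–10% rate was planned for prostacyclin-associated discontinuations. The 10% ceiling covers the whole study and is linked to how many subjects enter the i.v. period.
- By-visit summaries use the study-day windows in SAP Table 13, not this boundary. Early stoppers are discontinued from the study, so few scheduled measurements may fall in the window.
- The AE listing shows onset date and time and the action taken, so one or two cases could be reviewed individually. That helps a reader of the listing, but the by-period table remains wrong.

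**Conclusion.** The point holds with limited reach. The stated rule puts 0 to about 24 h on resumed oral drug into Period 2 for some early stoppers, and it gives no boundary when the Day 3 evening dose is not taken. About 1–2 of 18 subjects would be early stoppers on the borrowed rate, and not all of them would resume Uptravi early enough to have a misassigned window.

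A reader might infer more than the documents support:
- *Each early stopper adds 5.6 points to Period 2 incidence.* This does not follow. It needs a new event starting in the window, in a term not already counted for that subject in Period 2. A subject who stopped because of an AE in Period 2 is already in the any-AE row.
- *The main safety conclusions are distorted.* Protocol 6.2.2 analyses the main endpoints over all periods combined, and those displays are unchanged, as are the discontinuation counts.
- *All ECG, laboratory and blood pressure results are affected.* Only their by-period abnormality displays use the boundary.
- *The data for a corrected split are already collected.* Protocol 5.2.3 lists no Uptravi clock time for the Day 2 evening or Day 3 morning, SAP 5.5.1.2 uses the same four time points, and the general therapy record in protocol 5.2.2 lists dates only.

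**What to change.** This changes the analysis only and leaves every treatment rule as it is. In SAP 2.3 and Table 2:

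1. Define the end of Period 2 and the start of Period 3 as the first Uptravi intake after the subject's last i.v. infusion.
2. If there is no such intake, or its clock time is not recorded, use 12 h after the start of the last infusion. If only the resumption date is known and it conflicts with that time, use the scheduled dosing time on that date.
3. Footnote subjects who did not resume Uptravi. Without this, the fallback would place them under a Period 3 label that names Uptravi, and their later events could be read as occurring on oral drug.

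The cost is one extra derivation and an imputation rule, which is needed because the relevant Uptravi clock times are not listed for collection. Infusion start times are already in the CRF (protocol 5.1.4), so the fallback can be computed. Subjects who receive the third infusion and resume Uptravi as scheduled keep the same period dates.
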